## E. Conceptual Framework

Based on socioecological frameworks that encompass factors from individual to societal levels, we conceptualize the causes of treatment failure in children on ART under three broad, overlapping, and multifactorial themes of: 1) biomedical; 2) health system; and 3) socio-behavioral factors (Figure 2). Biomedical causes of treatment failure may include transmitted or acquired resistance, complex drug regimens that are difficult for caregivers to dispense, or failure to provide the appropriate weight-based dosing for younger children. Health system barriers include unresponsive centralized laboratory systems, undertrained health care workers, or drug stock outs. Socio-behavioral factors, such as adherence, disclosure, and stigma are critical to treatment success but complex for children who are dependent on caregivers. It is clear that a multifactorial approach is ultimately necessary to achieve optimal viral suppression rates in this population. Nonetheless, our current pilot proposal begins to address the biomedical and health systems components of treatment failure in children and provides the foundation for our larger vision of addressing the barriers to optimal viral suppression in this population.

As conceptualized in the Health Belief Model, we believe that timely feedback on viral suppression and DRM to both patients and providers, will act as “cues to action” driving their perceived severity and threat of their HIV disease progressing and their likelihood of taking positive actions, such as improving adherence or switching to more optimal ART regimens, to improve HIV disease status. Thus, our fundamental hypothesis is that earlier and more frequent VL monitoring will facilitate earlier and more appropriate clinical decision-making.

## RESEARCH METHODS

### A. Outcome Measure(s)

**Study Aim 1:** Our primary outcome for **Aim 1a** is rates of viral suppression (defined as VL <1000 copies/mL) at 12 months after enrollment for each child at the study facilities. Our secondary outcomes for Aim 1 are VL suppression and DRM patterns up to 5 years and time to viral suppression among those children without viral suppression at their 1st POC VL testing or newly initiating ART after POC VL testing implementation. We will also examine a set of process outcomes in this study, such as the feasibility of POC VL testing by describing the uptake, which we define as the proportion

of children undergoing VL testing within each group at the scheduled intervals. We will also examine the turn-around time for the VL testing results, retention-in-care, proportion of children switching ART, time to switch to 2nd or 3rd line ART, etc. for each arm. We hypothesize viral suppression rates will be higher among children with access to POC VL testing and time to viral suppression shorter compared to children with standard VL testing in the control arm one year after POC VL testing implementation. In **Aim 1b**, we intend to validate HIV-1 POC VL testing against current in-country gold standard VL testing by generating concordance/discordance rates and Cohen's kappa to determine assay agreement. We will also conduct sensitivity analyses to the concordance rates at lower thresholds of viral load cut offs for viral suppression (down to <40 copies/mL, the lower limit of quantification for the POC VL testing).

**Study Aim 2:** In our **Aim 2a**, we intend to evaluate the impact of targeted HIV DRM testing on viral suppression in the intervention arm and for all children newly initiating ART in both arms. We will describe the proportion of children tested for DRMs with significant mutations within each class of HIV drugs, e.g. NRTIs, NNRTIs, and PIs. We will also explore how sociodemographic, behavioral, clinical, and facility factors may be contributing to the DRM patterns we observe. We hypothesize that targeted DRM testing will shorten time to viral suppression among children on ART without viral suppression, high levels of antiretroviral DRMs in this population, and both individual factors, such as prior exposure to antiretrovirals, and facility-level factors, such as facility type, will predict the presence of DRMs. The same descriptive and analytic approaches will be used for data generated from the next-generation sequencing genotypic resistance and phenotypic resistance, especially to monitor emerging DRMs to DTG. In **Aim 2b**, we intend to determine and validate the test performance of a novel POC DRM assay, OLA Simple, against current in-country gold standard VL testing by generating concordance/discordance rates and Cohen's kappa to determine assay agreement.

**Study Aim 3:** In our **Aim 3a**, we intend to understand how our intervention functions and how policymakers might use tools to scale up POC VL and DRM testing by conducting focus group discussions (FGDs) and in-depth interviews with key informants. In these FGDs, we will assess policymakers' views on using systems engineering to inform decision-making. We will seek diverse opinions about the feasibility, acceptability, and scalability of systems engineering tool utilization, to understand how such tools would modify, support, enhance, or interfere with decision-making. In the KIIs, we will interrogate factors which acts as both facilitators and barriers to children achieving viral suppression and focus specifically on how POC VL and DRM testing may improve viral suppression. Furthermore, due to the on-going coronavirus disease 2019 (COVID-19) pandemic, we will query participants through study visit questionnaires and in-depth interviews to understand how the novel coronavirus disease 2019 (COVID-19) has impacted intervention delivery and participants' overall well-being. In addition, we will query particular logistical aspects of optimally operationalizing POC VL testing, e.g. how caregivers prefer to learn of the results or where facility staff see the most need for POC VL testing. These logistical aspects, such as the preferred approach to delivering results, result counseling content and methods, and provider reaction to results and additional capacity building needs for the providers and health facilities, need to be explored further in order to optimize implementation and scale up of POC testing. To understand how policymakers might use tools to scale up POC VL and DRM testing, we will use KIIs to understand how usable the model built in Aim 3b; we will cover domains of learnability, efficiency, memorability, error recovery, and satisfaction. In addition to qualitatively assessing these domains, we will

additionally collect a quantitative survey from the same participants to assess learnability, efficiency, memorability, error recovery, and satisfaction. For **Aim 3b**, we will estimate three main outcomes 1) the incremental cost-effectiveness of POC VL testing alone compared to standard laboratory testing, and 2) the effectiveness threshold needed to reach in order for a combination intervention scenario, which goes beyond POC VL testing alone (e.g. combines financial incentives for remaining virally suppressed), to be considered more cost-effective than POC VL testing alone, and 3) the optimal placement of POC machines in Kenya to minimize turnaround time. For the first two outcomes, we will calculate ICER as the ratio of the difference in costs divided by the difference in effects across simulations for the intervention compared to standard-of-care over a 10 year horizon. Consistent with guidelines, we will discount costs and health benefits at 3% annually, and consider ICERs below Kenya's per capita GDP to be cost-effective. We will perform extensive sensitivity analyses to identify influential assumptions. For the third outcome, we will create a *queuing model* – used in industrial engineering to model waiting times – to identify optimal placement of POC machines in Kenya. We will model the reduction in turnaround time and waiting time associated with placement of POC machines in a hub-and-spoke model, where select “hub” facilities (sites with a POC machine) and “spoke” (sites that send samples to a hub) facilities are chosen. We will also model a platform sharing model, in which POC machines rotate between different facilities within a sharing network. At different budget levels, we will identify the optimal number, placement, and network of POC machines.

[figure not shown]

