**Aim 3:** To understand how our intervention functions and how policymakers might use tools to scale up POC VL and DRM testing, by qualitatively exploring the barriers to achieving viral suppression and evaluating the feasibility of incorporating POC VL and DRM testing at programmatic scale using different sharing strategies to overcome of these barriers (**Aim 3a**) and to estimate the costs of implementing pediatric POC VL testing and DRM monitoring and the incremental cost-effectiveness per disability adjusted life year (DALY) averted, compared to standard clinical care, and determine the optimal placement of limited POC VL machines and DRM testing (**Aim 3b**).

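### Aim 3b outcome 2 asks when a combination beats POC VL testing, but the only ICER specified for it is against standard of care, and no threshold rule is given

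*Protocol*

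**What the plan says.** Protocol, Research Methods, A. Outcome Measure(s), Study Aim 3 lists three main outcomes for Aim 3b. Outcome 1 is "the incremental cost-effectiveness of POC VL testing alone compared to standard laboratory testing". Outcome 2 is "the effectiveness threshold needed to reach in order for a combination intervention scenario, which goes beyond POC VL testing alone", in order "to be considered more cost-effective than POC VL testing alone". By its own definition, then, outcome 2 sets the combination against POC VL.

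One method is then given for both: "For the first two outcomes, we will calculate ICER as the ratio of the difference in costs divided by the difference in effects". The rest of that sentence fixes the comparator and the time frame as "across simulations for the intervention compared to standard-of-care over a 10 year horizon". The decision rule is to "consider ICERs below Kenya's per capita GDP to be cost-effective", and "we will discount costs and health benefits at 3% annually".

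The other places that could settle the comparator do not:

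- Protocol, A. Specific Aims, Aim 3 names only the usual-care comparator: "the incremental cost-effectiveness per disability adjusted life year (DALY) averted, compared to standard clinical care".
- Protocol, Aim 3b: Modeling says that POC VL by itself and POC VL within a combination will both be simulated. It states no comparison between them.
- Protocol, F. Data Analysis Plan, Study Aim 3 speaks of the intervention and control arms and gives no rule for the threshold.
- SAP, Study Aim 3 places the aim outside its scope.

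The Outcome Measure(s) paragraph is therefore the only specification.

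**The concern.** Choosing between a combination and POC VL depends on what the combination adds in cost and in health over POC VL. Two ICERs that share a standard-of-care baseline do not settle that choice until a rule joins them, and the rule is missing. The comparator that is stated belongs to outcome 1.

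The threshold is the whole product of outcome 2, and it is meant for people deciding what to fund. If the same simulations can yield very different thresholds under an unwritten rule, the result cannot be interpreted. It could make a package look worthwhile that adds nothing to POC VL, or set the bar above what the GDP criterion asks.

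**Working it through.** **Inputs.** The protocol supplies the strategies, the stated comparator and the GDP cut-off. It gives no cost, effect, ICER or GDP amount, so there is no planned figure to reproduce and every number below is assumed.

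**Notation.** Costs and effects are increments over standard of care. POC VL has cost C1 and effect E1 (DALYs averted). The combination has fixed cost C2 > C1 and effect E2. L is GDP per DALY averted. The threshold is the smallest E2 that passes.

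**Three rules the text could lead to**

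- A, combination against POC VL, ICER at most L: (C2 − C1)/(E2 − E1) ≤ L, so threshold A = E1 + (C2 − C1)/L.
- B, combination against standard of care, ICER at most L: C2/E2 ≤ L, so threshold B = C2/L.
- C, combination's ICER against standard of care no higher than POC VL's: C2/E2 ≤ C1/E1, so threshold C = C2 × E1/C1.

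**Differences**

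- A − B = E1 − C1/L, which is POC VL's own net health benefit over standard of care.
- C − A = (C2 − C1) × (E1/C1 − 1/L).

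Both are positive when POC VL's ICER (C1/E1) is below L, zero when it equals L, and negative when it is above L.

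**Numbers.** Set E1 = 100 and L = 1.

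| POC VL ICER / L | C2/C1 | A | B | C |
|---|---|---|---|---|
| 0.25 | 1.5 | 112.5 | 37.5 | 150 |
| 0.25 | 2 | 125 | 50 | 200 |
| 0.5 | 1.5 | 125 | 75 | 150 |
| 0.5 | 2 | 150 | 100 | 200 |
| 0.75 | 1.5 | 137.5 | 112.5 | 150 |
| 0.75 | 2 | 175 | 150 | 200 |
| 1.0 | 1.5 | 150 | 150 | 150 |
| 1.5 | 1.5 | 175 | 225 | 150 |

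Second row in full: C1 = 25 and C2 = 50. A = 100 + 25 = 125, B = 50, C = 50 × 100/25 = 200. Check: A − B = 100 − 25 = 75.

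**Reading the table**

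- Rule B falls below POC VL's own effect of 100 whenever C2 < E1 × L. In the second row a package that costs twice as much and averts half as many DALYs would pass.
- Rule B can also be lenient without going that far. At 0.75 and 1.5 the threshold of 112.5 buys 12.5 extra DALYs for 37.5, an ICER against POC VL of 3.0 L.
- Rule C is an incremental test in disguise. C2 × E1 ≤ C1 × E2 is the same as (C2 − C1) × E1 ≤ C1 × (E2 − E1). The combination's ICER against POC VL must therefore be no higher than POC VL's own ICER. That is stricter than GDP whenever POC VL's ICER is below GDP.
- A standard-of-care baseline can still give rule A. Requiring E2 − C2/L ≥ E1 − C1/L rearranges to E2 ≥ E1 + (C2 − C1)/L.

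**The case against.** A reader might infer that the reported threshold is bound to be wrong. The documents do not support that, for four reasons.

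- The step from ICERs to threshold is unwritten. The sentence on standard of care may be a loose general definition, since it speaks of a single intervention while two strategies are in play.
- Rule B, the most damaging reading, conflicts with the outcome's own definition. A package that costs more and does less than POC VL cannot be the more cost-effective of the two.
- Rule C answers the outcome's wording literally and is coherent, only stricter.
- Both strategies are to be simulated, so the increments over POC VL follow by subtraction, and net benefit against standard of care gives rule A exactly.

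All of this stands, and it limits the point to a mismatch and an omission. It does not remove the point. The protocol applies the standard-of-care comparator to outcome 2 by name and specifies neither the subtraction nor net benefit. The fact that one reading is absurd and another is stricter than the stated cut-off is a reason to write the rule down.

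It is also fair that the sizes are assumed and that the closed form for rule A needs a fixed combination cost and effects in DALYs averted. The protocol does not define the unit of effectiveness for outcome 2, and in the agent-based model cost may move with effectiveness.

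**Conclusion.** The comparator stated for outcome 2 does not fit the question outcome 2 asks, and the rule that turns simulated costs and effects into a threshold is missing from both documents.

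If POC VL is cost-effective at GDP, holding the combination's ICER against standard of care to GDP makes the threshold too lenient by POC VL's own net health benefit. Ranking the two ICERs makes it stricter than the GDP criterion implies. In the illustration the same inputs give 50, 125 or 200. Protocol, B. Hypotheses expects POC VL with DRM testing to be cost-effective; if that carries over to POC VL by itself, these are the relevant directions. Above GDP they reverse, and at GDP the rules agree.

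The algebra is general for a fixed combination cost. The sizes are not predictions for this study. Severity is moderate: one of the three main Aim 3b outcomes is affected, while the randomized comparison, the primary outcome and power are not.

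**What to change.** In the Aim 3b text:

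1. Keep standard of care as the comparator for outcome 1.
2. For outcome 2, specify a full incremental analysis of standard of care, POC VL and the combination from the same simulations, with dominated strategies identified.
3. Define the threshold as the effectiveness at which the combination's ICER against POC VL, as the next-best non-dominated strategy, equals the GDP cut-off. Equivalently, it is where the combination's net health benefit equals that of POC VL.
4. State the unit of effectiveness. Use E1 + (C2 − C1)/L only if the combination's cost is fixed and effects are DALYs averted; otherwise solve for the threshold by simulation.
5. Say what will be reported if POC VL's own ICER exceeds GDP, because matching POC VL then does not make the combination cost-effective. In the last table row the rule A threshold of 175 has net health benefit 175 − 225 = −50, equal to POC VL's 100 − 150 = −50 and below standard of care at zero.

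The cost is a few sentences. No new data are needed, and both strategies are already to be simulated.

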## B. Description of Population to be Enrolled

The study population will be recruited from HIV-infected children and young adolescents age 1 to 14 years newly initiating or already receiving ART at the study facilities (n= approx. 700 children in total). Infants <1 year of age will not be included in the study as they frequently require more than 6 months of ART to suppress their initially high VL, and thus require specialized interpretation and management of VL results.

## C. Study Design and Research Methods

### Overall Study Design

We propose an open-label randomized, controlled study to pilot the use of POC VL testing and targeted DRM testing among HIV-positive children on ART age 1-14 years over a 12-month period in high-volume HIV treatment facilities in Kisumu, Kenya. We have chosen the study facilities to leverage existing POC technologies, as they are already equipped with GeneXpert® IV systems. Currently, these GeneXpert® systems are primarily being used for tuberculosis management. While validated for HIV VL monitoring, the technology remains to be tested for optimal integration into routine HIV clinical care. At each facility, eligible children will be randomized 1:1 to either receive the intervention testing, consisting of

quarterly POC VL testing and targeted DRM testing, or standard-of-care (SOC) testing based on the existing Kenyan national guidelines. We will follow the viral outcomes up to 24 months after enrollment for each child and compare VL suppression rates, defined as VL <1000 copies/mL by the Kenyan national guidelines, among intervention vs. control arms, accounting for pre-intervention VL suppression rates (**Figure 4**). Of note, after the 12-month study visit, the study will enter an observational-only phase to

continue to monitor for viremia and DRMs, especially among children on DTG-containing ART. During this observational-only phase of the project, participants will continue to receive testing, treatment, and other procedures as part of routine care, according to the standard-of-care then; study staff will not be providing any interventions, but only collect blood samples and administer questionnaires every 6 months up to 5 years of follow-up.

## Study Setting

The proposed study will occur in western Kenya in Kisumu County. Adult HIV prevalence in Kisumu is 19.9%, 3.4 times higher than the national prevalence. Kisumu County accounts for the second highest incidence of pediatric HIV infections, with 8,600 children estimated to be living with HIV and over 500 annual HIV-related deaths in children. The study will be implemented at low-resource, high-volume, high-HIV burden primary health care facilities and compare viral suppression rates in children randomized to intervention vs. control arms. These facilities are among the more than 70 health facilities in Kisumu County supported by the Family AIDS Care and Education Services (FACES), a PEPFAR/CDC-funded HIV prevention, care and treatment program run through a collaboration between the University of California, San Francisco (UCSF), the Kenya Medical Research Institute (KEMRI), and the Kenya Ministry of Health (CDC NU2GGH001947). FACES's unique model of technical support in direct collaboration with the local Ministry of Health (MOH) and CDC Kenya for provision of HIV care will allow implementation of the study interventions within government health facilities with strong technical support from FACES and study staff, thus promoting local ownership.

Table 1. Preferred 1st and 2nd line antiretroviral therapy regimens for children and adolescents in Kenya		
Age	Preferred 1st Line	Preferred 2nd Line
< 3 years	ABC+3TC+LPV/r	National referral for DRM testing/consultation
3-15 years		AZT-3TC-LPV/r
<35 kilograms	ABC+3TC+EFV	
> 35 kilograms	TDF+3TC+EFV	AZT+3TC+LPV/r or ATZ/r

Using a family model of care, FACES implements comprehensive pediatric HIV care and treatment services in accordance with the Kenyan MOH ART Guidelines. The latest guidelines, released in 2016, support initiation of ART for all individuals living with HIV, regardless of CD4 cell count or disease severity. Recommended 1st and 2nd line ART regimens are outlined in **Table 1**. Routine VL monitoring is offered through a laboratory network connected to a national, centralized laboratory and is recommended for children after six months of continuous ART and annually thereafter for those with VL <1000 copies/mL. Management of children with VL  $\geq$  1000 copies/mL includes adherence intensification and repeat of VL testing in three months followed by possible switch of ART for those who are still not virologically suppressed. Only those children on 2nd or 3rd line ART who continue to have viremia after adherence optimization, undergo DRM testing at a national reference laboratory. This testing process requires initial consultation with the Kenyan MOH HIV ART treatment committee, who then approves centralized DRM testing, receives the results, and eventually guides the local provider on management of the child failing their 2nd or 3rd line ART.


## Study methods

### Aims 1 & 2

**POC VL testing:** In this study, we propose the use of POC VL testing to optimize viral suppression rates in children and young adolescents. Several POC VL tests have undergone analytical performance evaluations and are becoming increasingly available in resource-limited settings. Of such POC VL tests, the GeneXpert® HIV-1 VL Assay developed by Cepheid is a leading test that has been validated and found feasible and reliable in rural African communities. It is an in-vitro test designed for rapid quantification of HIV-1 in human plasma from infected individuals over a range of 40 to 10 million copies/mL. The lower limit of quantification for the GeneXpert® VL assay is 40 copies/mL, with the lower limit of detection as low as 15 copies/mL. This assay uses reverse transcriptase polymerase chain reaction (PCR) technology to detect HIV in plasma, achieving a high sensitivity and specificity for quantification of HIV. The GeneXpert® HIV VL assay utilizes the existing GeneXpert® Instrument Systems. These systems consist of the instrument, personal computer, and preloaded software, and are already in place at the intervention facilities for detection of *Mycobacterium tuberculosis*. CDC Kenya has supported the purchase and maintenance of these GeneXpert® IV systems at some of these facilities and continue to provide ongoing training to MOH laboratory staff on its use. For facilities that do not have GeneXpert®, a hub and spoke lab networking model will be used to scale up POC VL. The sites with GeneXpert® technology will serve as the hub and near-by sites will transport their samples to the hub with quick turnaround times. Operationalizing such a model will foreshadow real-life implementation of such systems, where a hub and spoke model could be more feasible and sustainable. As such, the proposed study leverages the existing GeneXpert® technology already being supported by the Kenya MOH and CDC Kenya. In addition, the GeneXpert® VL assay kit is self-contained, including the necessary PCR reagents and supplies. The only additional tool required is a centrifuge to separate the plasma from whole blood which is available at all the intervention facilities in addition to trained laboratory staff capable of performing such procedures. This assay requires <1 minute of hands-on time with an average run time of 90 minutes reported from cartridge insertion to VL report generation. The GeneXpert® platform does not require batching tests and since the VL assay can be run with other tests simultaneously on the same machine, study use of the machine should not interfere with routine clinical use of the GeneXpert® machines. Ultimately, while the analytical performance of GeneXpert® HIV VL assay has been established, its clinical effect and optimal use remain to be determined. As POC VL testing becomes increasingly popular, rigorous evaluations, which include clinical outcomes, of such testing is necessary.

For those assigned to the intervention arm, our proposed POC VL testing will be done earlier than SOC, for those children newly initiating ART, and more frequently than SOC for children already on ART. For children newly initiating ART, we will conduct a POC VL test and DRM test pre-ART initiation, then POC VL only 3 months post-ART initiation, and every 3 months thereafter for up to 24 months. For children already on ART, we will conduct a POC VL test 3 months after their last VL test (or at the time of their next visit, if no VL testing has been done before), and every 3 months thereafter for up to 24 months. A blood sample will be collected by a study nurse during study visits every 3 months, which will be coordinated with their routine clinical visits; children on ART return to the clinic monthly for routine visits. Approximately 4mL (<1 tablespoon) of whole blood will be collected in EDTA plasma tubes from participating children for analysis of POC VL, potential DRM testing, and storage for any future studies. If phlebotomy of 4mL is difficult to achieve, we will aim to collect a minimum of 2mL of blood, using most of the sample for POC VL testing, and then prepare dried blood spots (DBS) for potential DRM testing if needed. All samples can be stored at room temperatures up to 25° Celsius, and in a cooler box if study facility temperatures rise above 25° Celsius, for up to 6 hours after sample collection. The samples will be processed within 6 hours of collection for plasma POC VL testing by existing lab staff already trained on GeneXpert® at intervention sites only after obtaining approval from the study nurses. Remaining plasma will be placed in aliquots and transported to the KEMRI-CDC laboratory in coolers for DRM testing or stored for any future testing. The study staff will return POC VL results to the ordering providers and caregivers within 24 hours of sample collection via text messages or phone (and paper results for providers). A generic message that lab results are available and a phone number to call free of charge for results will be sent to caregivers. Results will be given after verifying the caregiver and child's identity followed by appropriate counseling on viral load results. Name of the participant will not be included in the text messaging.

For those assigned to the control arm, VL testing will be conducted per national guidelines (as outlined above) through laboratory networking and transport to a centralized laboratory as the SOC. Children in the SOC arm who are newly initiating ART will have blood collected prior to ART initiation for future VL and DRM testing to be conducted at completion of study follow up. These results will be returned to clinical providers and patients/caregivers after the study. Additionally, in order to have comparable outcomes, POC VL will be conducted on ALL SOC participants at 12 and 24 months of follow up. Study nurses will prompt providers to order follow-up VL tests for those who qualify to ensure uptake of VL testing in both study arms.

We will batch test all stored samples for gold standard VL testing towards the end of the study period for both the arms (n= up to 700 samples), and generate concordance/discordance rates and Cohen's kappa to determine assay agreement. We will also conduct sensitivity analyses to the concordance rates at lower thresholds of viral load cut offs for viral suppression (down to <40 copies/mL, the lower limit of quantification for the POC VL testing). To conduct the in-country

gold standard HIV-1 VL testing (or quantification), we will build on our existing partnership with the KEMRI-CDC HIV Research Laboratory, led by [name], a collaborator on this proposal. The KEMRI-CDC facilities are located immediately outside of Kisumu. The KEMRI-CDC HIV Research laboratory utilizes state of the art HIV-1 quantification technologies by using Abbot m2000sp/RT, Roche CAP/CTM, and Roche C8800 systems (cite). Overall, the two main assay platforms, the Abbot vs. the Roche platforms, both perform extremely well, with subtle difference in accuracy and precision of each platform (cite). As we get closer to the time of running our samples for this validation, we will determine which specific platform to use depending on logistical aspects, such as current usage of the platforms. These platforms can run the assays with 0.5-1mL of plasma, which will already be stored in cryovials of this volume at the same facility. For each sample analyzed, we will receive printed reports noting exact quantification or below or above the limits of quantification.

**HIV DRM testing:** We will conduct targeted HIV DRM testing at the Kisumu-based KEMRI-CDC HIV Research laboratory using consensus sequencing on all plasma samples which lack viral suppression, defined as VL  $\geq$  1000 copies/mL per national guidelines. “Targeted” DRM testing will include DRM testing for each child on the first detection of such a VL and in children newly initiating ART. Subsequent samples from the same child on the same ART regimen will not be routinely retested, since costs of repeat DRM testing outweigh detection of new DRMs. Since approximately 65% of children achieve viral suppression currently in the FACES-supported facilities, including the study facilities, i.e. 35% have viremia VL  $\geq$  1000 copies/mL, we anticipate conducting DRM testing in at least 100 samples in participants in the intervention arm over the course of this pilot study. Such plasma samples, once processed from whole blood within 6 hours of collection, will be transported from the local health facility to the KEMRI-CDC laboratory the same day.

To conduct the HIV DRM testing, we are partnering with KEMRI-CDC, which has extensive facilities, including the HIV Research Laboratory led by [name], a collaborator on this proposal, located immediately outside of Kisumu. The KEMRI-CDC HIV Research laboratory utilizes Applied Biosystems (ABI) 3130x/ Genetic Analyzers to conduct its HIV drug resistance testing on 0.5-1mL of plasma. These analyzers have all steps automated, from polymer loading to sample injection to data analysis. This laboratory utilizes an optimized in-house assay to detect reverse transcriptase- and PI-based mutations. This validated, assay is broadly sensitive in genotyping HIV-1 subgroups, detecting all mutations classified in the IAS-USA mutations list, and more sensitive than commercially available assays for mixed viral populations. The KEMRI-CDC in-house assay can run samples from plasma or DBS; the ability to also use DBS is a key asset for our study, in case adequate volume of plasma cannot be obtained from our younger study population. DBS samples will be prepared by spotting 100  $\mu$ L of whole blood onto each of the preprinted circles on the DBS paper, then dried overnight at the local health facility at ambient temperature, and then transport wrapped DBS cards the next day.

At the KEMRI-CDC laboratory, the samples will be batched together daily, or at most weekly as this laboratory experiences a high volume of testing for other clinical and research projects. Results will be returned to the study staff within 24 hours of assay results, noting that the assay can take up to 24 hours to run. The DRM results report contains a list of the major and minor DRM genotypes as well as phenotypic interpretations, based on the scoring systems generated by the Stanford Genotypic Resistance Interpretation Algorithm. Study staff will then forward the DRM results to the ordering providers within 24 hours of their receipt and enter them into the patient file. Providers will use the results to guide patient management. Providers at the study facilities will undergo training on interpretation of the DRM testing results and study staff will work closely with facility leadership to assist providers in managing children with DRM including making any potential switches in accordance with national guidelines. As noted above, [name] has extensive background from the 2013 Kenya DRM survey in training and helping to build capacity for local HIV providers in understanding and interpreting DRM testing results. She will lead the standard operating procedures related to DRM testing results sharing with the facility providers and actively be involved in clinical decision-making as needed. We anticipate the turn-around time for the DRM testing to be 1-2 weeks at most; remarkably faster than the months-long process currently in place as SOC in Kenya. We anticipated that very few children in the control arm will undergo DRM testing as DRM testing is not currently recommended for children on 1st or 2nd line ART per national guidelines.

To further analyze emerging DRM for DTG, we will follow participants longitudinally after they reach the study primary endpoint (of 12 months after enrollment) and follow their routine care VL patterns while on DTG via an observational extension of this project for up to 5 years. If VL $>200$  copies/mL is detected by reviewing routine care records, study staff will contact the participant for either additional blood collection or permission to use any stored sample for next-generation sequencing (NGS) and phenotyping. All samples with VL  $\geq$ 200 copies/ml will be tested by NGS using the Illumina MiSeq platform using Primer ID in [name] lab at Seattle Children's Research Institute in Seattle, WA (the children's hospital affiliated with the University of Washington). This NGS method will allow for detection of low-frequency drug resistance mutations (minority variants), which may be present at baseline and/or at time of viremia. Sequences will be analyzed for HIV drug resistance mutations using the Stanford HIV drug resistance database (HIVdb) genotypic resistance interpretation system, and drug resistance mutations will be reported at detection thresholds of 1%, 2%, 5%, 10%, and 20%. The results

will be returned to the facility staff. For phenotyping resistance patterns, [name] lab at the University of Washington will perform phenotypic resistance testing for those samples with relevant genotypic mutations. His lab requires two 2-mL cryovials of plasma, which will be collected at the time of blood collection for NGS sample collection. Neither validated NGS nor phenotypic resistance testing is currently available in Kenya, thus, requiring shipment of samples to the U.S. During this observational-only phase of the project, participants will continue to receive testing, treatment, and other procedures as part of routine care, according to the standard-of-care then; study staff will not be providing any interventions, but only collect blood samples and administer questionnaires every 6 months up to 5 years of follow-up. However, if any irregularities in routine care are noted in regards to treatment or monitoring by study staff during this observational-only phase, study staff will alert the health facilities for possible routine care interventions.

OLA Simple-based DRM testing: We will evaluate the ability of OLA Simple to identify DRMs by comparing its results against DRM testing results from CS from study samples, as well as from the de-identified stored samples at the Kenya National HIV Reference Lab (NHRL), a key partner and stakeholder in future scale up of POC HIV DRM testing in Kenya. We will also evaluate the usability of OLA Simple when performed in the field in a clinical setting, bringing OLA Simple one step closer to being implemented as a POC DRM test. To increase efficiency, the OLA Simple testing will be conducted retrospectively, once the majority of samples to be tested have been collected, with direct observation from the [name] team. Nonetheless, to gain better insight into technician performance without direct supervision from the developers, we will also conduct a limited, prospective one-month long OLA testing towards the end of the participant follow-up. We will also partner with NHRL to cross-validate samples that have already undergone CS for clinical purposes and where leftover specimens are now stored and available for analysis at NHRL. These specimens are collected as part of routine clinical care from individuals experiencing viral failure, and are used for routine surveillance and evaluation of new test kits within the Kenya Ministry of Health. For NHRL, the use of their de-identified, stored specimens falls under the existing NASCOP-MOH routine lab validation procedures. Of note, results of the OLA Simple testing will not be returned to patients or providers, as this technology has not yet been approved for clinical use. The following procedures will be followed:

